10.5 Reporting SARs/SAEs

All maternal or neonatal SARs/SAEs, from the commencement of the trial treatment until discharge from hospital, must be recorded on the SAE form and faxed to BCTU on [name] within 24 hours of the research staff becoming aware of the event. Alternatively, the report can be emailed as a PDF attachment to the HOLDS email address from a NHS email account. The Principal Investigator (or other nominated obstetrician) is required to assign seriousness, causality and expectedness to the SARs/SAEs before reporting. All SARs/SAEs should be assessed for seriousness, causality and expectedness.

For each SARs/SAEs, the following information will be collected:

- full details in medical terms with a diagnosis, if possible
- its duration (start and end dates; times, if applicable)
- action taken
- outcome
- causality, in the opinion of the investigator*
- whether the event would be considered expected or unexpected* (refer to Reference Safety Information)

*Assessment of causality and expectedness must be made by an obstetrician. If an obstetrician is unavailable, initial reports without causality and expectedness assessment should be submitted to Trial Office by a healthcare professional (i.e., HOLDS midwife) within 24 hours, but must be followed up by medical assessment as soon as possible thereafter, ideally within the following 24 hours.

The local Principle Investigator and others responsible for the woman's or baby's care should institute any supplementary investigations of SARs/SAEs based on their clinical judgement of the likely causative factors and provide further follow-up information as soon as available.

SARs/SAEs still present beyond 28 days post-partum must be followed up until the final outcome is determined.

Once reported to the Trial office initial assessment of causality and expectedness will be made by the CI and confirmed by one of the obstetrician or neonatal co-applicants. BCTU will report all SARs/SAEs to the DMC following a timetable agreed by the DMC prior to trial commencement. The DMC will review these open, unblinded data for safety. BCTU will also report all SARs/SAEs to the Sponsor, the MHRA and the REC annually, and to the Trial Steering Committee (TSC), blinded to treatment allocation following a timetable agreed by the TSC prior to trial commencement. Local Investigators are responsible for reporting SARs/SAEs to their host institution, according to local regulations, but they do not need to inform the REC as this will be done by BCTU as detailed above.

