8.4 Breastfeeding

There are no restrictions on breastfeeding for women recruited to the HOLDS trial.

Process	Time	CRF	Person responsible
Confirm eligibility	When delay confirmed	Randomisation form	GCP and HOLDS trained obstetrician
Consent	Following confirmation of eligibility	Consent form	GCP and HOLDS trained obstetrician or midwife
Randomisation telephone call	Following confirmation of consent	Complete randomisation form	HOLDS trained obstetrician, midwife, student midwife or Maternity Support Worker
Prescription of drug	Following randomisation	Prescription chart	HOLDS trained obstetrician
Study treatment allocation	Following prescription of drug	Randomisation form and in medical notes	HOLDS trained midwife or obstetrician
Labour data collection	From commencement of study treatment until after birth	Labour form	HOLDS trained midwife
Birth outcome data collection	After discharge	Birth and discharge form	HOLDS midwife

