9.2 Secondary maternal outcomes

Clinical outcomes

- Epidural use during labour
- Duration of first, second and third stages of labour
- Time to birth from randomisation
- Mode of birth (spontaneous vaginal birth (SVB), instrumental or CS)
- Degree of perineal trauma (first, second, third and fourth degree)
- Reason for CS and decision to delivery interval for CS
- Confirmed urinary retention requiring catheterisation and pulmonary oedema
- Tachysystole (uterine contractions greater than 5 in 10 mins for 20 minutes) requiring reduction in oxytocin and/or tocolysis
- Hyperstimulation (uterine contractions greater than 5 in 10 mins for 20 minutes resulting in non-ressurring or abnormal fetal heart rate)
- Fetal blood sampling (FBS) during labour or significant STAN event (for those Units that use ST waveform analysis for intrapartum fetal monitoring)
- Abnormal cardiotocogram leading to immediate birth without fetal blood sample
- Incidence of possible maternal morbidity (anaphylaxis, pulmonary oedema, postpartum haemorrhage, shoulder dystocia, chorioamnioitis, uterine rupture/hysterectomy)
- Active management of third stage of labour
- Length of time after birth in hospital [days]
- Admission to HDU/ITU
- Maternal death

Process outcomes

- Time from randomisation to commencement of allocation
- Total oxytocin dose
- Time to maximum oxytocin rate
- Maximum oxytocin dose reached

9.3 Neonatal secondary outcomes include:

- Gender and birthweight
- Apgar score at 5 minutes

- Arterial cord blood gases when collected
- Breastfeeding rates on discharge from hospital
- Length of time after birth in hospital [days]
- Resuscitation
- Reason for neonatal review on ward (excluding routine baby check)
- Reason for admission to neonatal unit (NNU) and level of care received (level 1,2,3)including intensive care
- Duration of respiratory support
- Days to full oral feeds
- Seizures
- Neonatal encephalopathy (SARNAT grade)
- Therapeutic hypothermia (cooling) if required
- Intrapartum still birth
- Early neonatal death (within seven days of birth)

10 Safety Monitoring Procedures

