10.4 Expected SAEs

In addition to the definition of a SAE given in section 10.1.3, the following events (listed for convenience, but are not limited) do not have a causal association with the trial drug and should be reported as a SAE:

Maternal outcomes

• uterine rupture/ hysterectomy

- postpartum haemorrhage that triggers the Massive Obstetric Haemorrhage protocol, including blood transfusion
- maternal admission to HDU/ITU- requiring critical care level 2 or 3 as defined by national criteria categorised by us
- maternal death

Neonatal outcomes

- unexpected provision of neonatal intensive care
- neonatal seizures
- neonatal encephalopathy
- the need for neonatal therapeutic hypothermia and
- Intrapartum stillbirth
- neonatal death

For details on how to report SAEs please see Section 10.5 – Reporting of SARs/SAEs.

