11.1 Data collection forms

Data for the purpose of assessing the efficacy and safety within the HOLDS trial will be collected from the participating maternity units by the clinical team responsible for the participants care on a number of data collection (case report) forms (CRFs). Data required for the primary and the majority of secondary outcomes are objective measures which are routinely collected for clinical purposes and will be transcribed from woman's records, which collectively are the source data.

Paper forms will be used to confirm eligibility (prior to telephone randomisation), to document informed consent and to collect data during labour. The outcome data should be entered directly onto the database by those with on-line access. It can be completed in paper form and returned to the HOLDS Trial Office to be entered centrally onto the online database.

There is no need to hold any identifiable data in the Trial Office – the participating sites will collect the woman's NHS and hospital number and both may be used in the process of collecting missing data. The Trial Office will only have a unique identifier for the participant.

Data from the Case Report forms described earlier should be entered into the secure online HOLDS database as soon as possible after collection by the HOLDS research midwife or obstetrician. These clinical personnel will be allocated personal usernames and passwords that will only allow access to entry forms for the trial participants who are being treated at their site. Alternatively, paper forms can be sent to the HOLDS Trial Office for central input.

Data validation is built into the online database. Range, date and logic checks are performed at the point of data entry. Email reminders will be sent to the research midwives for missing data forms, missing data or data inconsistencies. This will be followed by phone contact.

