11.3 Definition of the End of Trial

The trial will be deemed complete when the last recruited woman has given birth and outcome data collected and entered onto the data collection system.

For participants the End of Trial is end of discharge from maternity unit or death for the mother and discharge from maternity or neonatal unit or death with 7 days for the baby.

12 Statistical methods and analysis

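### Early neonatal death is defined to seven days, but no stated procedure establishes vital status at day 7 for a baby discharged earlier

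*Combined protocol and SAP*

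**What the plan says.** Section 9.3 lists among the neonatal outcomes "Early neonatal death (within seven days of birth", a window fixed in time and not tied to where the baby is. Four other places decide whether that window can be observed.

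- Section 10.5 requires maternal and neonatal serious events to be reported "from the commencement of the trial treatment until discharge from hospital". Section 10.4 lists "neonatal death" as a reportable event without a time limit of its own, so the 10.5 window governs it.
- In the data-collection table of section 8.5 the last row is "Birth outcome data collection", timed after discharge, on the Birth and discharge form. No earliest day is given.
- Section 11.3 ends the baby's participation at "discharge from maternity or neonatal unit or death with 7 days for the baby".
- Section 11.1 says that data for the primary and most secondary outcomes "will be transcribed from woman's records, which collectively are the source data". Sites collect the woman's "NHS and hospital number and both may be used in the process of collecting missing data". No identifier for the baby and no record linkage is described.

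Section 10.5 also says "SARs/SAEs still present beyond 28 days post-partum must be followed up until the final outcome is determined".

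**The concern.** To report deaths within seven days, the trial must know whether each baby was alive on day 7. Postnatal stay is itself an outcome measured in days, and no minimum stay is set, so discharge before day 7 is allowed for throughout. Once such a baby has gone home, no stated step looks again.

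Safety for babies is a stated objective (section 6.3), and section 4.8 of both appended product summaries lists foetal distress, asphyxia and death among the adverse reactions. Section 10.7.3 sends every fatal serious event to the Data Monitoring Committee for continuous review. A death at home on day 4 falls outside the reporting duty and need never enter that route. The same holds for a readmission with, say, seizures, although section 10.1.3 counts hospitalisation as serious. Nor would the gap show up as missing data: a baby recorded as alive at discharge looks complete, and the sensitivity analyses in section 12.2.3 concern the primary outcome.

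**Working it through.** The plan gives no figure to reproduce. The check compares time windows, followed by an illustration of scale.

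**Windows side by side**

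| Item | Section | Runs until |
|---|---|---|
| Early neonatal death | 9.3 | day 7 after birth |
| Serious event reporting, baby | 10.5 | discharge from hospital |
| Birth and discharge form | 8.5 | after discharge, no earliest day |
| Baby's end of trial | 11.3 | discharge, or death within 7 days |

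**Can any other text close the gap?**

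1. The 28-day sentence in 10.5 applies to events still present. It extends the follow-up of known events and does not detect new ones after discharge.
2. The clause on death in 11.3 can be read two ways. If the earlier of discharge and death applies, a baby who goes home leaves the trial at discharge. If the intention is to count every death to day 7, the clause conflicts with the limit in 10.5 and still gives no means of finding the death.
3. A form completed some days after discharge may pick up a later death, but only if the site happens to know of it.

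**Length of the uncovered period.** For a baby discharged on day d, with d below 7, the uncovered time is 7 − d days. Discharge on day 2 leaves 7 − 2 = 5 days.

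**Scale, by assumption only.** The documents give neither a neonatal death rate nor the share of deaths that follow discharge. Take N = 1500 births (sections 7.3 and 12.1: 1500 women, singleton pregnancies), an assumed early death rate r of 0.5 to 2 per 1000, and an assumed share s after discharge of 10% to 50%.

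- Early deaths = N × r
- Deaths after discharge = N × r × s
- Chance of at least one = 1 − (1 − r × s)^N

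| r | s | Early deaths | After discharge | Chance of at least one |
|---|---|---|---|---|
| 0.0005 | 0.10 | 0.75 | 0.075 | 7% |
| 0.001 | 0.25 | 1.5 | 0.375 | 31% |
| 0.002 | 0.50 | 3.0 | 1.5 | 78% |

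These are totals over both arms and cover deaths only. Readmissions with a serious event would be additional.

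**The case against.** The strongest reply is that the babies at highest risk are already covered, and for most of them that is right. A reader might infer that a baby transferred elsewhere for intensive care or cooling is lost. The documents do not support this: unexpected intensive care and therapeutic hypothermia are listed events in section 10.4, and section 10.5 requires the outcome and further follow-up information for them. A reader might also think that a death on the neonatal unit on day 9 is mishandled. It is excluded from an outcome that is by definition early death, but it is still a reportable fatal event and goes to the Data Monitoring Committee. The gap is therefore confined to babies who go home before day 7 without a reportable event.

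It is also tempting to argue that, if the high dose lowers the caesarean rate, its babies go home sooner and harm in that arm is hidden. The documents give no lengths of stay. With assumed stays of 1–2 days after vaginal birth and 2–4 days after caesarean, the difference is 0 to 3 days. Section 12.1 plans for a fall from 32% to 24%, so 8 babies in 100 would change group, and mean observation time would shift by 0.08 × 0 = 0 to 0.08 × 3 = 0.24 days. That does not support a claim of material bias between arms.

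Finally, the flow chart in section 8.8 could not be read in the available text, and the case report forms and the separate analysis plan are not among the documents. A day-7 check could sit in one of these. Even so, the limit in 10.5 would still need to be reconciled with 9.3.

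**Conclusion.** The mismatch stands. Followed as written, the protocol has no planned way to detect a death, or a readmission with a serious event, between discharge and day 7 in a baby who went home without a reportable event. It would go too far to say that such deaths cannot be captured, because a site may learn of one before completing the form. The accurate statement is that capture is unplanned, so an outcome labelled as seven-day death is in effect death before discharge.

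Few events are at issue: 0.08 to 1.5 deaths in the whole trial under the assumed rates. This is a question of completeness in a key safety outcome and not of power, and the primary outcome is unaffected. With expected totals of only 0.75 to 3 early deaths under the same assumptions, a single missed death would still change the safety statement noticeably. The point should be corrected.

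**What to change.** 1. In section 10.5, run the baby's serious event window to day 7 after birth or discharge from hospital, whichever is later.
2. In section 8.5, state that the baby's part of the Birth and discharge form is closed no earlier than day 7, after a check of available records for vital status and readmission.
3. Align section 11.3 with this and keep the fixed seven-day definition in section 9.3. Widening 9.3 to count deaths before final discharge would make the window depend on length of stay, so it is not advised.

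If the sponsor will not look past discharge, rename the outcome neonatal death before discharge, which needs only a change of wording.

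The cost is a delay of a few days in completing the form and one short look-up per baby. The look-up may need the baby's identifier as well as the mother's, since section 11.1 names only hers, and it may miss events at other hospitals. That limit should be stated when the outcome is reported.

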10.6 Reporting SUSARs

SAEs categorised by the local investigator as **both** suspected to be related to the trial drug **and** unexpected are SUSARs, and are subject to expedited reporting. All SUSARs must be recorded on the SAE Form and faxed to the BCTU on [name]. Alternatively, the report can be emailed as a PDF attachment to the HOLDS email address from a NHS email account, within 24 hours of the research staff becoming aware of the event. The Chief Investigator (CI) or nominated individual will undertake urgent review of SUSARs within 24 hours of reporting and may request further information immediately from the patient's clinical team. The CI will not overrule the causality, expectedness or seriousness assessment given by the local investigator. If the CI disagrees with the local investigator's assessment, further clarification and discussion should take place to reach a consensus. If a consensus cannot be reached, both the opinion of the local investigator and the CI should be provided in the report to the MHRA and the REC.

The BCTU will report all SUSARs to the MHRA and the main REC. If the SUSAR resulted in death or was life-threatening this will be done within 7 days of the initial report being received or within 15 days for any other SUSAR. If information is incomplete at the time of initial reporting, or the event is ongoing, the BCTU will request follow-up information, including information for categorisation of causality, from the local investigator and will send the follow-up information to the MHRA and main REC within an additional 8 days for fatal or life-threatening SUSARs and as soon as possible for any other events.

10.7 Safety reporting responsibilities

10.7.1 Local Principal Investigator (or nominated individual in PI's absence)

- To record all safety events that occur in the women taking part in the trial. This includes serious, expected or unexpected adverse events, unless defined as outcomes above
- Medical judgement in assigning expectedness and causality to SAEs
- To fax SAE forms to BCTU within 24 hours of becoming aware, and to provide further followup information as soon as available
- To report SARs/SAEs to local committees if required, in line with local arrangements
- To sign an Investigator's Agreement accepting these responsibilities

10.7.2 Chief Investigator (or nominated individual in Cl's absence)

• To assign initial causality and expected nature of SAEs where it has not been possible to obtain local assessment

- To review all events assessed as SAEs in the opinion of the local investigator for causality and expectedness and agree with obstetric/ neonatal co-applicants
- Alert the DMC Chair if concerned

10.7.3 Birmingham Clinical Trials Unit

- To prepare annual safety reports to the REC, TSC and MHRA
- To prepare SAE safety reports for the DMC following a timetable agreed by the DMC prior to trial commencement, or as requested by the DMC
- To report all fatal SAEs to the DMC for continuous safety review

10.7.4 Trial Steering Committee (TSC)

- To provide independent supervision of the scientific and ethical conduct of the trial on behalf of the Trial Sponsor and funding bodies
- To review data, protocol deviations, outcome capture rates, adverse events (during treatment and up to the end of follow-up)
- To receive and consider any recommendations from the DMC on protocol modifications

10.7.5 Data Monitoring Committee (DMC)

- To review (initially at approximately six-monthly intervals) overall safety and morbidity data to identify safety issues which may not be apparent on an individual case basis
- To recommend to the TSC whether the trial should continue unchanged, continue with protocol modifications, or stop

10.7.6 Sponsor

- To ensure safety reports and delegated duties are completed by key individuals
- Ensure safety reports/issues are reported appropriately
- Ensure compliance with regulatory approvals and legislation
- Maintain oversight of safety issues throughout trial

11 Data Management

11.1 Data collection forms

Data for the purpose of assessing the efficacy and safety within the HOLDS trial will be collected from the participating maternity units by the clinical team responsible for the participants care on a number of data collection (case report) forms (CRFs). Data required for the primary and the majority of secondary outcomes are objective measures which are routinely collected for clinical purposes and will be transcribed from woman's records, which collectively are the source data.

Paper forms will be used to confirm eligibility (prior to telephone randomisation), to document informed consent and to collect data during labour. The outcome data should be entered directly onto the database by those with on-line access. It can be completed in paper form and returned to the HOLDS Trial Office to be entered centrally onto the online database.

There is no need to hold any identifiable data in the Trial Office – the participating sites will collect the woman's NHS and hospital number and both may be used in the process of collecting missing data. The Trial Office will only have a unique identifier for the participant.

Data from the Case Report forms described earlier should be entered into the secure online HOLDS database as soon as possible after collection by the HOLDS research midwife or obstetrician. These clinical personnel will be allocated personal usernames and passwords that will only allow access to entry forms for the trial participants who are being treated at their site. Alternatively, paper forms can be sent to the HOLDS Trial Office for central input.

Data validation is built into the online database. Range, date and logic checks are performed at the point of data entry. Email reminders will be sent to the research midwives for missing data forms, missing data or data inconsistencies. This will be followed by phone contact.

11.2 Long-term storage of data

Storage will be authorised by BWNFT as Sponsor following submission of the end of trial report.

Principal Investigators are responsible for the secure archiving of essential trial documents for their site, according to the local policy at that site. All essential documents will be archived for a minimum of 25 years after completion of trial.

11.3 Definition of the End of Trial

The trial will be deemed complete when the last recruited woman has given birth and outcome data collected and entered onto the data collection system.

For participants the End of Trial is end of discharge from maternity unit or death for the mother and discharge from maternity or neonatal unit or death with 7 days for the baby.

12 Statistical methods and analysis

12.1 Sample size

The sample size is informed by the pilot study¹, recent survey of practice and Cochrane review⁶. The pilot study indicated a CS rate of 32% in the standard dose group (95%CI: 19% to 45%), whilst responses from the survey of practice (n=60 responses) indicate that a 25% relative reduction would be considered an important clinical difference to change practice. Detecting a difference of this size assuming a standard dose group rate of 32% (8% absolute reduction down to 24%) with 90% power (p=0.05) will require 1320 women. If the control group rate is lower, e.g. 24%, recruiting 1500 women would give 80% power to detect the same relative difference. We have selected the latter figure as our target sample size. The independent Data Monitoring Committee (DMC) will review the event rate to monitor the control rate on a six-monthly basis throughout the recruitment period.

